#### Qualitative:

In the proposed study, individual feedback phone interviews will be conducted following post-intervention assessment to qualitatively assess participants' experience of all procedures. All interviews will be conducted within two weeks of the end of the intervention period to maximize internal consistency. It is anticipated that each interview will last approximately 15-20 minutes.

MPIs [name] and [name] have developed draft questions for the feedback interview guide. Consistent with the timeline submitted in the proposal, the study team will finalize the feedback interview guide and protocol by month 4 of study year 1. Per recently published guidelines for maximizing impact of qualitative research in feasibility studies to inform an RCT, broad feedback interview question categories include: 1) intervention content and delivery; 2) trial design, conduct, and process; 3) treatment outcomes; and 4) measures and assessment burden. Sample questions include:

#### Intervention Content and Delivery (MBRT and SME groups)

- If you invited a friend to participate in the training, what would you tell them?
- What aspects of the training were *most* helpful for you?
- What aspects of the training were *less* helpful for you?
- What were the biggest obstacles to fully engaging in or completing the training?

#### Trial Design, Conduct, and Process (all groups)

- What was your reaction to being randomized to the \_\_\_\_\_ group?
- Were reminder calls/contact with coordinator helpful (too much/ too little)?
- What feedback do you have to help improve the experience of future officers who will take part in the same study?

#### Outcomes (MBRT and SME groups)

- What changes, if any, did you notice in your resilience after completing the training?
- Did the training affect your ability to cope with stress?
- Has the training impacted your day-to-day work?

#### Measures and Assessment Burden (all groups)

- What was your experience with the computerized measures (i.e., assessment burden, clarity of questions, ease of administration process)?

- What was your experience with the dried blood spot collection (i.e., burden, clarity of instructions)?

Individual phone feedback interviews will be conducted using standardized methods, as described by Flick. Each interview will be conducted by a trained research assistant, and will be audio recorded and transcribed. LEOs will be instructed to refrain from disclosing unnecessary personal information. Informed consent procedures will clearly state that participation in feedback interviews is voluntary, and participants will be instructed to share only what they choose to. They will be reminded that all content will be de-identified to protect their anonymity.

A thematic analysis approach will be used to explore participant experiences with the goal of understanding feasibility, acceptability and impact of the assessments, protocol, and intervention. Analyses will consist of: 1) familiarization, 2) initial coding, 3) creating themes, 4) reviewing themes, 5) defining and naming themes, and 6) data interpretation. MPI [name] and two trained research team members will initially independently review feedback interview data. Emerging themes will be used to develop a coding scheme and the team will then independently apply the codes from the finalized code structure. The coding team will meet regularly to review coding and resolve differences by in-depth discussion and negotiated consensus to ensure inter-rater reliability. A dynamic approach will be used by analyzing the first wave of feedback interview data following initial MBRT and SME groups, which may result in changes to intervention or trial procedures, then reassessing the impact of these changes on participants' experience of assessments, protocol, and/or intervention. We will also assess the equivalence of experience across sites, and confirm self-report measurement sensitivity based on the relationship between qualitative reports of change and quantitative results on outcome measures.

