## **9.6 Data Analyses**

### Quantitative:

Following best practice guidelines including CONSORT feasibility guidelines and past research, we will measure sensitivity (using a relative efficiency approach) and

responsiveness to change (examining within-group change over time). Relative efficiency analyses will be used to establish that our outcome measures are sensitive to differences between our treatment arm of focus (MBRT) and our other two arms - an active control arm (SME) and a no-treatment control arm (NIC). Therefore, sensitivity analyses will focus on assessing the degree to which outcomes are sensitive to study arms and not whether change is significant. Sensitivity to differences for MBRT compared to SME and NIC will be assessed by examining the relative efficiency of each outcome variable for MBRT versus SME and NIC separately. We will calculate the relative efficiency for MBRT versus SME by conducting one-way, between-subjects Analysis of Covariance (ANCOVA) analyses with MBRT versus SME as the independent variable and each outcome variable at post-training as the dependent variable; we will include study site and gender as covariates. We will also conduct ANOVAs using the same independent and dependent variables to ensure that all inferential tests are conducted and identify any potential Type II Errors among the ANCOVAs. We will then divide the *F*-statistic for each behavioral (BlueTeam/departmental use of force; individual indicators of use of force as well as a composite score of use of force using the individual indicators), physiological (C-RP, IL-6, IL-10, TNF- $\alpha$ ), and self-report (aggression, alcohol misuse, depression, suicidal ideation, trauma symptoms, burnout, and psychological resilience) outcome by the largest *F*-statistic among these analyses, such that the larger the number, the more sensitive that outcome is to the impact of MBRT relative to the active control group.

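### The feedback interviews are meant to confirm measure sensitivity, but as planned they bear on responsiveness in the trained arms and give no evidence on MBRT versus NIC

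*Combined protocol and SAP*

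**What the plan says.** Section 9.6 (Quantitative) separates two properties. Sensitivity is assessed between arms: the analysis is to establish that "our outcome measures are sensitive to differences between our treatment arm of focus (MBRT) and our other two arms", by "examining the relative efficiency of each outcome variable for MBRT versus SME and NIC separately", using F-statistics on post-training outcomes. Responsiveness is change over time within a group, assessed in the MBRT arm. Objective 4 in the Précis also lists the two as distinct things to confirm.

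Section 9.6 (Qualitative) introduces the interview topics with "Sample questions include" and describes the questions as drafts for a guide still to be finalised. The category on change is headed "Outcomes (MBRT and SME groups" and holds three questions:

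- The first, on resilience, reads "What changes, if any, did you notice in your resilience after completing the training".
- The second, on coping, reads "Did the training affect your ability to cope with stress".
- The third, on the job itself, reads "Has the training impacted your day-to-day work".

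Two other categories are for all groups. They cover randomisation, contact with the coordinator, suggestions for improvement, the computerised measures and the blood spot kit. Neither asks about change.

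The last paragraph on the thematic analysis then says the team will "confirm self-report measurement sensitivity based on the relationship between qualitative reports of change and quantitative results on outcome measures". It names no comparison of the reports between arms, no statistic and no criterion for confirmation.

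**The concern.** A claim to confirm sensitivity, in this plan's own vocabulary, is a claim about how well a measure separates MBRT from SME and from NIC. Relating an officer's account of change to that officer's scores is a different exercise. It asks whether two self-reports from one person agree. With no listed change question for NIC, there is also no untreated reference for how often officers report change without any training.

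This matters because the trial exists to choose outcome measures for a larger efficacy trial. A report stating that the interviews confirmed a measure's sensitivity would lend it support of a kind the interviews did not supply.

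**Working it through.** **1. Who is asked about change.** Section 3 gives N = 104, allocated 2:1.5:1, with stated arms of 47, 35 and 22. The ratio gives 104 × 2/4.5 = 46.2, 104 × 1.5/4.5 = 34.7 and 104 × 1/4.5 = 23.1, so the stated sizes are reproduced to within about one or two officers. Arms with a listed change question: 47 + 35 = 82, and 82/104 = 79%. Arm without one: 22/104 = 21%. These are allocation figures; interviews are voluntary.

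**2. Definitions against interview content.**

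| Property in Section 9.6 | What it needs | What the interviews offer as planned |
|---|---|---|
| Sensitivity, MBRT v NIC | Reports of change from both arms, compared | Reports from MBRT only |
| Sensitivity, MBRT v SME | Reports from both arms, compared | Same questions in both arms, but no comparison by arm planned |
| Responsiveness | Change within trained officers | Report-to-score relationship, which fits |

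**3. How the questions are framed.** Two of the three ask whether the training had an effect. The first is anchored in time, to after the course, and allows for no change. All three presuppose a course, and Section 5.1 gives NIC officers none, so none can be put to that arm as worded.

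**4. Illustration that the two quantities differ.** All inputs here are assumed except the arm sizes and the 20% attrition. Arm sizes after attrition: 47 × 0.8 = 37.6, 35 × 0.8 = 28 and 22 × 0.8 = 17.6, taken as 38, 28 and 18. Reported and measured change each have SD 1 and correlate 0.5 within arm. An arm that improves shifts by 0.5 SD on both. F is unadjusted for site and gender.

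- Pooled MBRT+SME correlation, for a difference d between those arms, with p = 38/66 = 0.576: (0.5 + p(1−p)d²)/(1 + p(1−p)d²).
- Mean F with 1 and v degrees of freedom: v(1 + λ)/(v − 2), where λ = d² n₁n₂/(n₁ + n₂).

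If only MBRT improves, d = 0.5:

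- Correlation: (0.5 + 0.061)/(1.061) = 0.53.
- MBRT v SME: λ = 0.25 × 38 × 28/66 = 4.03, so mean F = 64 × 5.03/62 = 5.19.
- MBRT v NIC: λ = 0.25 × 38 × 18/56 = 3.05, so mean F = 54 × 4.05/52 = 4.21.

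A simulation of 4,000 trials per scenario gave similar values:

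| Scenario | Report–score r (MBRT+SME) | Mean F v SME | Mean F v NIC |
|---|---|---|---|
| All arms improve equally | 0.50 | 1.09 | 1.03 |
| MBRT and SME improve, NIC does not | 0.50 | 1.05 | 4.12 |
| Only MBRT improves | 0.53 | 5.26 | 4.11 |

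The correlation hardly moves while F changes four- to five-fold. Because 0.5 was put in, the table cannot say how strong agreement will be in this trial. It shows only that agreement in the trained arms does not track separation between arms.

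**The case against.** The strongest reply is that the sentence uses the word sensitivity loosely. It states its own operation, a relationship between reported and measured change, which resembles the correlation with the global impression of change that the plan files under responsiveness. Restricting the change questions to trained arms fits that use: the schedule in Section 6.1 also limits the Global Impression of Change to MBRT and SME. This stands as an account of what the interviews can do, and it is the reason the wording should change. It does not make the word right in a section that defines it otherwise.

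Several limits also stand. The questions are samples, so the final guide could add a change question for NIC, although nothing says it will. MBRT and SME officers get the same questions, so their reports could be compared. The F-statistic analyses do not draw on interview data. Section 1.1 has benchmark sensitivity and responsiveness values decide which measures are kept, and no rule selects an outcome on interview confirmation.

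A reader might infer that the interviews would appear to confirm the measures even if MBRT did nothing. The documents do not support that. The plan looks at a relationship, not at how many officers report benefit; reports of benefit alongside flat scores would count as disagreement. A reader might also infer that all three questions ask officers to credit the training, but the first does not.

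On masking, Section 3 keeps staff who collect qualitative data from the unique ID codes. It does not say whether those coding the interviews work without sight of questionnaire results.

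**Conclusion.** The concern holds in a limited form. As planned, agreement between interview and questionnaire bears on responsiveness or convergent validity in MBRT and SME. It gives no evidence on MBRT versus NIC, one of the plan's two sensitivity comparisons, and could inform the other only if reports were compared by arm. The arm without a listed change question is 22 of 104 officers (21%) by allocation.

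This rests on the definitions in Section 9.6 and on the final guide following the draft categories. It does not rest on the illustrative correlation of 0.5. Only the confirmation claim is affected. It would go too far to say that the quantitative sensitivity analysis or the choice of outcomes is compromised, or that no NIC officer will in fact be asked about change.

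**What to change.** In Section 9.6 (Qualitative), replace the claim to confirm sensitivity with: *describe agreement between interview and questionnaire reports of change, by arm, as supporting evidence on responsiveness*.

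In the final guide, and in all interviews still to be held:

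- Ask all three arms, including NIC, one neutrally worded change question before any training-specific question. For example: *Since your first assessment, what changes, if any, have you noticed in your resilience or in how you handle stress?*
- Keep the existing training questions afterwards for MBRT and SME.
- Code the answers before the coders see questionnaire results.
- Report the coded answers by arm.

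NIC officers are already to be interviewed, so no new visit is needed. The cost is a slightly longer NIC interview. Section 3 schedules first-cohort interviews alongside that cohort's post-intervention assessment, so any already completed will lack the item, and the report should say so. Section 9.6 already allows procedures to change after the first wave of interviews. If the guide cannot be changed, the rewording alone removes the unsupported claim.

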## 10. DATA COLLECTION AND QUALITY ASSURANCE

### 10.1 Data Collection Forms

Self-report data will be collected using Qualtrics, a data collection software platform that operates on a secure server. A dried blood spot kit will be used to collect blood spots. Each participant will be identified by a unique ID code and data will be linked to unique ID. Personal identifying information (i.e., names and phone numbers) will only be used on forms such as the informed consent or telephone contact logs, where they are essential. Any forms with identifying information will be kept secure and separate from data. Tracking forms linking names and unique study ID codes will be stored on Box, a secure, HIPAA-compliant data storage system, accessible only to IRB-authorized research staff.

### 10.2 Data Management

Data will be stored in REDCap and Qualtrics. REDCap is a secure (HIPAA-compliant) internet-based survey and data management software system housed on a secure server at Oregon Health and Science University. Qualtrics is a data collection software platform supported by Pacific University that operates on a secure server.

## **10.3 Quality Assurance**

### **10.3.1 Training**

Goals and Strategies: All study staff will be trained in NIH Good Clinical Practice. Interventionists will undergo intensive MBRT or SME training. Ongoing oversight and supervision of all intervention procedures will occur throughout the trial, including weekly review of MBRT and SME sessions and clinical supervision. We will hone intervention protocols and session coding procedures, train coders, and adapt the Adherence and Competence Scale for use with both MBRT and SME to ensure parallel domains are assessed, and that fidelity is equivalent, both across sites and between MBRT and SME interventions. Specifically, four of the eight sessions (50%) will be randomly selected from each MBRT and SME group to be rated by two independent coders, who will be randomly assigned to session. Raters will be trained until they meet  $\geq .75$  interrater reliability, then meet for periodic calibration meetings to prevent rater drift.

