subsequently maintain  $\geq 85\%$  overall fidelity (including session content coverage, presence of main themes, and global skills). Interrater reliability between all coders will be  $\geq .75$ , which is an established criterion for excellent reliability.

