MBRT and SME groups will be led by separate interventionists, with at least masters level training in mental health or a related field, and matched for level of education and experience. MBRT interventionists will have previous training in and experience with MBRT or related interventions (e.g., MBSR, MBCT or MBRP), and will undergo intensive training, weekly clinical supervision, and regular meetings with MPIs to discuss fidelity and other clinical issues. Drs. [name], [name], and [name] are clinical psychologists with combined knowledge of psychoeducational protocols, MBIs, first responder populations, trauma, substance abuse, and other psychosocial outcomes. Given the importance of internal validity of interventions in RCT research, careful attention will be given to intervention adherence and consistency across sites, with all sessions being audio and video recorded. Under the supervision of [name], [name], and consultant [name], advanced graduate students at both study sites will review four randomly selected sessions from each MBRT cohort to assess intervention fidelity, adapting the MBRP Adherence and Competence measure used in previous trials. Drs. [name], [name], and [name], as well as consultant [name], will do the same for each SME cohort. Drs.

[name], [name] and [name] will provide weekly supervision to all interventionists to ensure fidelity and minimize drift. Participants in the NIC condition will not engage in a training; therefore, the administration of this group will only entail scheduling and meeting NIC participants for data collection.

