## 5. STUDY INTERVENTIONS

### 5.1 Interventions, Administration, and Duration

Both MBRT and SME will include psychoeducation, gentle movement exercises focused on stress reduction and fitness, and weekly homework assignments, and will be matched for time and assigned homework.

MBRT will be delivered in groups of 10 to 13 law enforcement officers, in 8 weekly sessions of 1 hour each, with the exception of weeks 1 and 7 which are extended 7- and 4-hour classes, respectively, for a total of 17 intervention hours. The extended session, modeled after MBSR, is intended to provide an immersive training experience. The session will contain a series of mindfulness practices, including body scan, mindful movement, and walking and breath-focused

meditations. The session will focus primarily on formal mindfulness practices, in contrast to inclusion of discussion and psychoeducational components contained in other MBRT sessions.

If state, local and university allow Sessions 1 and 7 to be in-person, they will be conducted at the study sites. If not, they will be conducted using the online Zoom platform. Any MBRT in-person intervention sessions will be held in reserved rooms able to accommodate up to 25 people, and large enough to comply with social distancing guidelines - specifically, the Psychology Research Lab in Portland, and at UNM Department of Psychology in Albuquerque. All MPD groups will be conducted remotely. Online groups will be facilitated via Zoom. MPI [name] and Co-Is [name] and [name] will oversee MBRT interventionist training. [name] co-developed MBRT, and is an expert in MBIs with first responders; [name] and [name] have facilitated, trained and supervised MBIs, and have collaborated on multiple MBI-related NIH trials.

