SME will be delivered as a weekly, 8-week, 1.5 hour class, except for weeks 1 and 7 which are extended to 4-hour classes, for a total of 17 intervention hours, with weekly homework (amount matched to MBRT), and gentle movement exercises. The content focuses on psychological, physiological, and dietary effects of stress, time management techniques, fitness, sleep hygiene, nutrition, and factors mitigating effects of stress. [name] (SME developer) will provide input and support to ensure interventionists are trained to fidelity. Training will be conducted by trainers approved by [name], with experience conducting SME and training interventionists. MPI [name], a licensed clinical psychologist with experience facilitating stress management groups, will oversee SME training with support from [name]. Potential adverse effects include: minor aches or strains from mindful movement practices, and mild emotional distress completing self-report measures or exposure to the socially evaluative cold pressor task challenge procedures.

MBRT and SME groups will be led by separate interventionists, with at least masters level training in mental health or a related field, and matched for level of education and experience. MBRT interventionists will have previous training in and experience with MBRT or related interventions (e.g., MBSR, MBCT or MBRP), and will undergo intensive training, weekly clinical supervision, and regular meetings with MPIs to discuss fidelity and other clinical issues. Drs. [name], [name], and [name] are clinical psychologists with combined knowledge of psychoeducational protocols, MBIs, first responder populations, trauma, substance abuse, and other psychosocial outcomes. They each have extensive experience developing, implementing, supervising, and assessing similar interventions.

Given the importance of internal validity of interventions in RCT research, careful attention will be given to intervention adherence and consistency across sites, with all sessions audio and video recorded. Under supervision of Drs. [name], [name], [name] and consultant [name], advanced graduate students at both study sites will review four randomly selected sessions from each MBRT and SME cohort, adapting the MBRP Adherence and Competence measure used in previous trials. Drs. [name], [name] and [name] will provide weekly supervision to all interventionists to ensure fidelity and minimize drift.

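### Three sections describe the fidelity coding differently, and the unstratified draw of sessions can leave a group with neither extended session coded

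*Combined protocol and SAP*

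**What the plan says.** Section 10.3.1 states that "four of the eight sessions (50%) will be randomly selected from each MBRT and SME group". On the raters, it adds that these sessions are "to be rated by two independent coders, who will be randomly assigned to session". Coders are trained to an interrater reliability of at least .75 and hold calibration meetings.

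Section 3 says that, under supervision, "advanced graduate students at both study sites will review four randomly selected sessions from each MBRT cohort to assess intervention fidelity". The next sentence names doctoral staff and a consultant who "will do the same for each SME cohort".

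Section 5.1 says that, under supervision, "advanced graduate students at both study sites will review four randomly selected sessions from each MBRT and SME cohort".

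On session format, section 5.1 describes weekly one-hour MBRT classes "with the exception of weeks 1 and 7 which are extended 7- and 4-hour classes, respectively, for a total of 17 intervention hours". Of the extended MBRT session it says: "The session will focus primarily on formal mindfulness practices, in contrast to inclusion of discussion and psychoeducational components contained in other MBRT sessions". SME also extends weeks 1 and 7, to four hours each, around 1.5-hour weekly classes.

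The numeric criteria are in section 1.1, Objective 3: interventionists reach 90% fidelity in training and then maintain at least 85% overall, and coders reach .75. Equivalence of fidelity across sites and between MBRT and SME is an aim in Précis item 3.2 and in section 10.3.1. It has no numeric margin.

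**The concern.** Fidelity is one of the trial's primary feasibility objectives, and its value lies in comparison: MBRT against its active control, and site against site. Two things weaken that comparison.

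First, staff who follow section 3 and staff who follow section 10.3.1 would produce different data. If doctoral staff rate SME and students rate MBRT, a difference in fidelity between the arms, or the lack of one, could reflect who rated rather than what was delivered. A reliability of .75 does not by itself exclude a shift in mean score between two kinds of rater, unless they rate common sessions from both arms. The choice between *cohort* and *group* also changes how much is coded.

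Second, nothing in the sampling rule separates extended from weekly sessions. The extended sessions hold most of MBRT's contact time. In hybrid cohorts they are the only in-person sessions (section 3), while Madison groups are always remote (section 5.1). They are therefore where MBRT delivery can differ by site, and a group's score can be formed without them.

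**Working it through.** **The plan's own figures.** Four of eight sessions is 4/8 = 50%, as stated. MBRT hours: 6 × 1 + 7 + 4 = 17. SME hours: 6 × 1.5 + 4 + 4 = 17. Both reproduce. Extended sessions make up 11/17 = 64.7% of MBRT hours and 8/17 = 47.1% of SME hours.

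**The three descriptions side by side.**

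| Section | Sampling unit | MBRT rated by | SME rated by |
|---|---|---|---|
| 3 | cohort | graduate students | doctoral staff and a consultant (plain wording), or students whom they supervise |
| 5.1 | cohort | graduate students | graduate students |
| 10.3.1 | group | two coders, random assignment | two coders, random assignment |

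On the plain wording of section 3, the three cannot all be followed.

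**Cohort or group.** The MBRT arm has 47 officers in groups of 10 to 13 (sections 3 and 5.1). 47/13 = 3.6 and 47/10 = 4.7, so four groups fit, giving 4 × 8 = 32 sessions. Four per group is 16/32 = 50%. The timetable in section 3 uses *cohort* for the two training waves; on that meaning, four per cohort is 8/32 = 25%.

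**The draw within one group.** There are C(8,4) = 70 equally likely draws.
- Neither extended session: C(6,4)/70 = 15/70 = 21.4%
- Exactly one: 40/70 = 57.1%
- Both: 15/70 = 21.4%

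Coded MBRT time in a group ranges from 4 h (23.5%) to 13 h (76.5%), with mean 8.5 h.

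**Site level.** Portland and Madison each recruit 26. At 2:1.5:1 that gives 26 × 2/4.5 = 11.6 MBRT officers per site, about one group each. If groups are site-specific, the chance that at least one of these two sites has no extended MBRT session coded is 1 − (55/70)² = 38%.

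**Pooled over MBRT.** The chance that no extended session is coded in any of four groups is (15/70)⁴ = 0.2% (4.6% with two groups, 0.05% with five). The chance that week 1, or week 7, is never coded in any of four groups is 2 × 0.5⁴ − (15/70)⁴ = 12.3%.

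**Stratified draw: one of weeks 1 and 7, three of the six weekly classes.** Inclusion probability is 1/2 for each extended session and 3/6 = 1/2 for each weekly one, as now. Expected coded hours are (7 + 4)/2 + 3 × 1 = 8.5 for MBRT and 4 + 3 × 1.5 = 8.5 for SME, also as now. Coded MBRT time is then 7 or 10 h, and the 21.4% falls to 0.

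**The case against.** A reader might infer that the plan does assign different raters to the two arms. The documents do not establish that. The first of the two sentences in section 3 already casts senior staff as supervisors, so the second may mean that they supervise the SME review. Section 5.1 reads that way, and sections 5.1 and 10.3.1 both describe reviewers shared across arms. What stands is a contradiction on the plain wording, with confounding as its consequence only if that wording is followed.

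A reader might also infer that the 85% benchmark could be met without any extended session being coded, and cite the chance that at least one of four groups has none: 1 − (55/70)⁴ = 62%. That is the wrong unit. The benchmark is set for interventionists, and section 3 has the same pair leading MBRT at all sites, so the relevant figure is the 0.2%. A simple random draw is also unbiased for the per-session mean. Nor is there a numeric arm-equivalence benchmark to miss, and extended weeks are not unique to MBRT; its seven-hour length and its content are.

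Sessions are all recorded, and section 10.3.1 provides weekly review and supervision. The extended sessions are therefore not unobserved, but this oversight is not tied to the fidelity score.

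Finally, the stratified draw does not make either extended session more likely to be coded, and it removes the 21.4% chance that a group has both. That is correct, and it is why week 1 and week 7 need balancing across groups. Section 5.1 speaks of the extended session in the singular; if only one of the two is immersive, the stratified draw alone does not guarantee that one.

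**Conclusion.** The point holds as an inconsistency to reconcile and a sampling rule to tighten. Sections 3, 5.1 and 10.3.1 do not agree on the sampling unit or, on plain wording, on the raters. The possible consequences are a halving of the sessions coded (25% against 50%, if *cohort* means wave and there are four MBRT groups) and confounding of arm with rater type (if section 3's split is followed).

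The unstratified draw carries a 21.4% chance per group that neither extended session is coded. This matters for group scores and, assuming site-specific groups, for site scores at Portland and Madison (38% that at least one has none). The pooled 85% benchmark is not threatened. The number of groups is derived from the stated arm and group sizes; the plan does not state it.

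**What to change.** Put the section 10.3.1 rule into sections 3, 5.1 and 10.3.1 alike: four sessions from every MBRT and SME group, and one pool of coders randomly assigned to session, with each coder rating both MBRT and SME. State whether the senior staff named in section 3 rate or supervise.

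Draw one session from weeks 1 and 7 and three from the six weekly classes. Balance week 1 and week 7 across groups where possible, so that both are covered within each arm. The two arms need not use identical week numbers; the plan does not say that their content corresponds week by week. Report fidelity by arm, site and session type.

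The cost is protocol wording. The number of coded sessions under section 10.3.1 and the expected coding hours do not change. Groups that would have drawn no extended session have longer recordings to code: 7 or 10 hours instead of 4 for MBRT. At a site with a single MBRT group, only one of the two extended sessions is then coded. Coding both plus two weekly classes would close that gap, but takes 13 of 17 hours for MBRT and 11 of 17 for SME.
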